## 7.12 Safety Follow-up Visit

Approximately 30 days after the final dose of TTI-621 ( $\pm$  2 days), the following will be performed. If treatment-emergent abnormalities are present at the end-of-treatment visit, repeat pertinent labs or studies:

- symptom driven physical examination and ECOG score
- body weight
- vital signs
- serum chemistries
- hematology
- TSH (only for subjects in the nivolumab combination cohort)
- serum for ADA analysis; subjects who are seropositive at safety follow-up, should be monitored at least quarterly for 1 year post study to assess persistence of antibodies
- status of unresolved AEs

## 7.13 Long-term Follow-up (Expansion Phase Only)

For a period of 1 year following the safety follow-up visit, subjects treated in the expansion phase will be contacted at least quarterly ( $\pm 1$  week) via routine clinic visit and/or telephone call to assess the following:

- subsequent anticancer therapies
- status of any ongoing/chronic AEs that were treatment-emergent
- persistence of ADA in those subjects who seroconverted
- date of disease progression (if not documented on study)
- survival status

## 7.14 Procedures for Special Tests

### 7.14.1 Disease Assessment

Disease assessments for individual malignancy types are detailed in Appendix D. Table 3.

#### *Response Criteria*

Tumor response assessment for lymphomas (including PTCL) in both the escalation and expansion phases will utilize the Lugano Classification (Cheson et al., 2014), including the 2016 refinement of these criteria (Cheson et al., 2016). A response will be defined as an objective status of partial remission (PR) or complete remission (CR) for subjects evaluated by computed tomography (CT)-based criteria and complete metabolic response (CMR) or partial metabolic response (PMR) for subjects evaluated by positron emission tomography -CT based criteria. For CTCL, a response will be defined as PR or CR in any of the organ systems individually (skin, viscera, blood or lymph nodes). Additionally, a global response incorporating each organ system will be compiled per the Olsen criteria (Olsen et al., 2011). Radiographic disease assessments for CTCL and PTCL will be submitted for central review for those subjects enrolled to phase 1b Part 3. The subjects enrolled to phase 1b Part 4 will not require submission of scans for central review in real time but might be requested by sponsor retrospectively.

For the additional malignancies in the expansion phase, the following classification systems will be employed:

- AML and ALL – Revised Recommendations of the International Working Group for trials in AML (Cheson et al., 2003)

- CLL – International Workshop on CLL update of the NCI 1996 Guidelines (Hallek et al., 2008)
- MDS/MPN – An International Consortium Proposal of Uniform Response Criteria for Myelodysplastic/Myeloproliferative Neoplasms (MDS/MPN) in Adults (Savona et al., 2015)
- Multiple Myeloma – International Uniform Response Criteria for Multiple Myeloma (Durie et al., 2006)
- CTCL – Clinical Endpoints and Response Criteria in Mycosis Fungoides and Sezary Syndrome (Olsen et al., 2011)
- SCLC – Adaptation of the Immune-Related Response Criteria: irRECIST (Bohnsack et al., 2014)

### *Pseudoprogression or Indeterminate Response*

Some therapeutic agents, particularly immunotherapeutics, display different patterns of anti-tumor response, which may include a period of increasing tumor burden followed by a response, stable disease followed by slow decline in tumor burden, or even a response in the presence of new lesions (Cheson et al., 2016; Chow, 2013; Wolchok et al., 2009). Immune-mediated responses may take longer to manifest than those from cytotoxic agents. In other cancer settings, a phenomenon called “tumor flare” or pseudoprogression has also been described, in which increased contrast enhancement and hyperintensity is observed on posttreatment MRI scans (fluid - attenuated inversion recovery, or FLAIR) which represents a biologic effect on the tumor and its microenvironment and which stabilizes or diminishes over time (Batchelor, 2012).

In order to avoid falsely assigning disease progression during the expansion phase of the study, a subject whose radiologic disease assessment is indicative of progression may, at the discretion of the Investigator and Medical Monitor, be considered “Indeterminate” in the case report forms and continue on treatment pending a repeat scan 4 to 6 weeks later, if all of the following criteria are met:

- absence of symptomatic or clinical progression
- stable performance status
- adequate tolerance to TTI-621 therapy
- treating beyond progression does not delay an intervention felt to be in the subject’s best interest

If the second confirmatory scan indicates unequivocal disease progression, the subject will be discontinued from treatment. The date of the first scan indicating progression will be used for analysis purposes. If however the second scan indicates a reduction in tumor burden or stable disease from the baseline scan, the subject may continue on treatment in the absence of unacceptable toxicity or other reason for treatment discontinuation.

Notwithstanding, the Investigator is free to remove the subject from treatment at any time during the study if it is felt to be in the subject's best interest.

#### 7.14.2 PK

In both the escalation and expansion phases (Part 2), serial blood sampling will take place in conjunction with the first and sixth weekly infusion of TTI-621 (i.e., Days 1 and 36 of study) to estimate the PK profile of TTI-621. Subsequent sampling after the first week will be limited to "trough" levels (30 minutes pre-dose). A sample will also be taken at EOT.

For phase 1b Part 3 only, serial blood sampling will take place in conjunction with the first and eighth weekly infusion of TTI-621, a time at which mandatory intra-subject dose intensification for newly enrolled subjects is anticipated to be completed. This sampling will be performed to evaluate the PK profile of TTI-621 following dose-intensification, and after repeat dosing. Subsequent sampling will be limited to "trough" levels at Week 9 through Week 16 inclusive. A sample will also be taken at EOT.

For phase 1b Part 4, for subjects enrolled in cohorts without priming doses, serial blood sampling will take place in conjunction with the first and sixth weekly infusion of TTI-621 (i.e., Days 1 and 36 of study) to estimate the PK profile of TTI-621 with further dosing optimization. For subjects enrolled in cohorts with priming dose regimen under phase 1b Part 4 receiving a single priming dose on Week 1, serial blood sampling will take place on Week 2, following administration of the highest stable dose and on the sixth weekly infusion of TTI-621 to estimate the PK profile of TTI-621 with further dosing optimization. Subsequent sampling for all phase 1b Part 4 cohorts, will be limited to "trough" levels at Week 9 through Week 16 inclusive. A sample will also be taken at EOT.

If there is a delay in infusion administration (i.e., duration of TTI-621 infusion is greater than 60 minutes), the end-of-infusion PK sample should be drawn at the time the infusion is complete (prior to flush). However, all subsequent timepoints should

not be adjusted and should be collected relative to the start of TTI-621 infusion as summarized in [Table 7-2](#).

Whole blood will be collected at each time point and prepared as outlined in the separate Laboratory Manual.

**Table 7-2: Summary of PK Sampling Times**

Week	Day	Nominal Time	Allowable Time Window
N	1	Pre-infusion (within 30 min)	± 15 min
	1	EOI (60 min) §	+5 min
	1	T + 2 hr §	± 15 min
	1	T + 4 hr §	± 15 min
N	2	T + 24 hr §	± 6 hrs
N	4	T + 72 hr §	± 24 hrs
N	1	trough (30 min pre-infusion)	± 15 min
EOT		Within 1 week following final dose	

EOI = immediately after the end of infusion (i.e., prior to flush)

EOT = end of treatment

N = any week where the listed timepoints are applicable

§ Relative to the start of first TTI-621 infusion

CCI

- CCI [REDACTED]  
[REDACTED]
- [REDACTED]  
[REDACTED]
- [REDACTED]  
[REDACTED]
- [REDACTED]  
[REDACTED]

## 8 PLANNED ANALYSES

A separate Statistical Analysis Plan will provide final specific details on the analytical methods and data displays.

### 8.1 Study Endpoints

#### 8.1.1 Escalation Phase

*Primary*

- Incidence and severity of AEs

*Secondary*

- PK profile, PD, ADA

#### 8.1.2 Expansion Phase, Part 2 and Part 3

*Primary*

- Incidence and severity of AEs

*Secondary*

- PK profile, PD, ADA
- Overall response rate, duration of response, and progression-free survival
- Part 3: CTCL and PTCL: organ system overall response rate – 2 analyses within each cohort

#### 8.1.3 Expansion Phase, Part 4

*Primary*

- Incidence and severity of AEs

*Secondary*

- PK profile, PD, ADA
- Overall response rate and duration of response
- CTCL: organ system overall response rate

## 8.2 Analysis Populations

### *Safety Analysis Set*

The Safety Analysis Set will be used for the analysis of safety data in this study and will consist of all subjects who receive at least 1 dose of TTI-621.

### *Full Analysis Set*

The Full Analysis Set will serve as the primary population for all efficacy-related data, with the exception of the analysis of overall response, for which the Response-Evaluable Set will be primary, and the Full Analysis Set will be secondary. The Full Analysis Set is a subset of all enrolled subjects, with subjects excluded for the following reasons:

- failure to receive at least 1 dose of TTI-621
- lack of baseline data for those analyses that require baseline data

### *Response-Evaluable Set*

The Response-Evaluable Set will serve as the primary population for the analysis of overall response. The Response-Evaluable Set is a subset of the Full Analysis Set, with subjects excluded if they have no post-baseline assessment of overall response.

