Pharmacodynamic measurements and biomarkers will be summarized using summary statistics and may be displayed graphically as appropriate. Subgroup analyses, which will be pre-specified in the SAP, may be conducted in the expansion phase of the study to explore the relationship between measures of anti-tumor activity and selected baseline biomarkers.

*Phase 1b Part 3-Specific Analyses*

Each of the 2 additional cohorts (CTCL and PTCL) will be evaluated separately for the potential to be further studied using the Simon 2-stage design. For the first stage, a total of 18 response-evaluable subjects will be reviewed in each cohort; if 2 or fewer responders are observed, enrollment in the respective cohort will be terminated. Otherwise, enrollment will continue to the second stage and an additional 17 subjects will be enrolled for a total of 35 response-evaluable subjects per cohort. At the end of the second stage, if 6 or fewer responders per cohort are observed, the drug will be rejected for further testing in this indication. The safety and efficacy assessments outlined above will be summarized for each cohort separately. If more than the required number of response-evaluable patients are available (i.e., >18 or >35), the first 18 or 35, respectively, would be used.

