### **3.5 Number of Subjects**

The dose escalation portion of the study is estimated to enroll up to 36 subjects with an advanced lymphoma. The dose expansion phase 1b (Part 2) will enroll 12–15 subjects per cohort type. If preliminary evidence of clinical benefit is observed in association with acceptable tolerability, one or more hematologic disease-specific cohorts may be expanded up to a maximum of 40 subjects. For the dose expansion phase 1b (Part 3), the number of subjects in the CTCL and PTCL cohorts will be enrolled based upon a Simon optimal 2-stage design with a maximum of 35 subjects in each cohort.

In addition, approximately 25 subjects will be enrolled for the phase 1b dose optimization (Part 4). The total number of subjects enrolled in the study is approximately 285 subjects (see [Section 8.3](#) for details).

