### 7.1 Screening Period

Informed consent may be obtained within 30 days prior to Day 1, after which it is recommended that the subject be re-consented. The following procedures will be performed after written informed consent has been obtained and within 14 days prior to the planned start of treatment unless otherwise noted:

- physical examination including review of systems (breast/chest, extremities, head/ears/eyes/nose/throat, lymph nodes, musculoskeletal, pulmonary and skin), and height
- body weight

- ECOG performance status (see [Appendix B](#))
- vital signs including heart rate, respiratory rate, and body temperature
- baseline disease assessment as indicated for the specific primary malignancy (see [Section 7.14.1](#) and [Appendix D. Table 3](#)) within 28 days prior to the planned start of treatment. CTCL: mSWAT, CAILS (local disease only) and central photographs.
  - Leukemia and lymphoma with marrow involvement: bone marrow aspirate for routine morphology, flow cytometry, CD47 expression and receptor occupancy (not required for Part 4)
  - CTCL: photographs of tumor lesions will be captured at the clinical site(s) using standardized photographic equipment, methodologies and services provided by Canfield Scientific, Inc. (Parsippany, New Jersey). Further detail for study photography will be provided in the supplied Canfield User Manual
- CTCL and PTCL (Part 3 only): Radiographic disease assessments for CTCL and PTCL will be submitted for central review (central results are not required for enrollment). Please refer to the Imaging Manual. Part 4 will not require submission of scans for central review in real time but retrospective submissions might be requested by sponsor.
- CTCL and PTCL (Part 3 only): Tumor tissue will be submitted for central review for subjects with CTCL (not including SS) and PTCL to confirm the diagnosis (central disease confirmation not required for enrollment). For subjects with SS, peripheral blood is acceptable. Archival tissue may be provided. Refer to the Laboratory Manual for additional details.
- resting 12-lead ECG
- hepatitis B (HBsAg and HBcAb) and C (HCV Ab) panel
- serum pregnancy test for women of childbearing potential

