## 7.11 End-of-Treatment Visit

Within 1 week following the final dose of TTI-621 (or at the time of premature discontinuation of treatment), the following procedures will be performed:

- physical examination and ECOG score
- body weight
- vital signs
- disease assessment (if not performed within the last 8 weeks)
- QOL by FACT-G (all subjects) and SKINDEX29 (CTCL only)
- resting 12-lead ECG
- serum for PK
- serum chemistries
- hematology

- coagulation panel
- TSH (only for subjects in the nivolumab combination cohort)
- urinalysis
- serum for ADA analysis
- biomarkers (see Study Manual for details of sample preparation and shipping):
  - serum for cytokine/chemokine panel (not required for Part 4)
  - whole blood for innate and adaptive response assay (not required for Part 4)
- AEs
- concomitant medications
- peripheral blood and blood smear for central pathology for SS patients (Part 3 only). Refer to the Laboratory Manual and to [Appendix D. Table 3](#) for additional information.

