#### *Expansion Phase Part 3: CTCL and PTCL Cohorts*

For the phase 1b (Part 3) expansion cohorts for CTCL and PTCL, the cohort size has been selected based upon a Simon optimal 2-stage design, with the low and high boundaries of the response rate being 10% (not effective) and 30% (warrants further study) respectively, and a power of 90% and an alpha of 0.05. The calculations were performed using PASS 14 (NCSS, 2015) and the Optimum design chosen. The total sample size is 35 subjects per cohort under the scenario described below. For the first stage, a total of 18 subjects will be enrolled in each cohort. At the end of Stage 1, if 2 or fewer responders are observed per cohort, enrollment in this cohort will be terminated, otherwise, enrollment will proceed to the second stage and an additional 17 subjects will be enrolled per cohort for a total of 35 subjects per cohort. At the end of the second stage, if 6 or fewer responders are observed per cohort, the drug will be rejected for further testing in this indication. The probability of early termination (PET) = 0.734 at the end of the first stage if the true response rate is less than 10%.

N1	R1	PET	N	R	Average N	Alpha	Beta
18	2	0.734	35	6	22.53	0.047	0.098

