#### **8.4.7 CTCL and PTCL Cohorts**

##### **Phase 1b Part 3: CTCL and PTCL Cohorts**

Radiographic disease assessments for CTCL and PTCL will be centrally reviewed. Each of the 2 cohorts (CTCL and PTCL) will be evaluated separately for the potential for further study using the Simon 2-stage design. For the first stage, a total of 18 response-evaluable subjects will be reviewed in each cohort; if 2 or fewer responders are observed per cohort, enrollment in that cohort will be terminated. Otherwise, enrollment will proceed to the second stage and an additional 17 response-evaluable subjects will be enrolled per cohort for a total of 35 response-evaluable subjects per cohort. At the end of the second stage, if 6 or fewer responders are observed per cohort, the drug will be rejected for further testing in this indication. If more than the required number of response-evaluable patients are available (i.e., >18 or >35), the first 18 or 35, respectively, would be used.

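### The Part 3 Simon rule is stated on response-evaluable subjects in some places and on enrolled subjects in others, under a cap of 35, and the SAP does not name the set for the count

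*Protocol*

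**What the plan says.** **Rule on evaluable subjects.** Protocol 8.4.7 says: "For the first stage, a total of 18 response-evaluable subjects will be reviewed in each cohort". It then asks for 17 further evaluable subjects and uses the first 18 or 35 if more are available. The synopsis (Part 3-specific analyses) has the same first stage, but its second stage mixes the two bases: "an additional 17 subjects will be enrolled for a total of 35 response-evaluable subjects per cohort".

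**Rule on enrolled subjects.** Protocol 8.3 says: "For the first stage, a total of 18 subjects will be enrolled in each cohort", with a total of 35 subjects. SAP 1.2.4 repeats that text.

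**Cap.** Protocol 3.5 describes "a Simon optimal 2-stage design with a maximum of 35 subjects in each cohort". The synopsis cohort table also gives up to 35 for CTCL and for PTCL.

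**Sets.**
- Protocol 8.2, on overall response: "for which the Response-Evaluable Set will be primary, and the Full Analysis Set will be secondary". It forms the Response-Evaluable Set from the Full Analysis Set "with subjects excluded if they have no post-baseline assessment of overall response".
- Protocol 8.4.6 runs efficacy on the Full Analysis Set and adds the Response-Evaluable Set for response.
- SAP section 2 makes the Full Analysis Set (all treated) primary for efficacy and the Response-Evaluable Set secondary. Its version keeps subjects who left unassessed because of early progression or safety, and drops other unassessed withdrawals.
- SAP 3.7.1 defines the response rate on both sets and counts missing responses as non-responses. It does not mention the Simon rule.

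**Interim looks.** SAP 1.2.6 plans no interim efficacy analyses, although SAP 1.2.4 stops enrollment on Stage 1 response counts.

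**The concern.** This is the trial's only formal efficacy decision rule, and its two versions cannot both be followed once one subject goes unassessed. With 35 enrolled and one unassessed, there are 34 evaluable subjects. Either the cap is broken or the evaluable total is not reached.

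The choice of set also has a direction. The protocol's definition removes a subject with no post-baseline assessment even when the reason is early progression, death or toxicity. The next subject takes that place in the first 18. If the removed subjects are non-responders, replacing them can only move the decision towards go.

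The end-of-treatment visit limits the problem but does not remove it. Protocol 7.11 requires a disease assessment there only if none was done in the previous 8 weeks, and protocol 7.1 allows the baseline assessment up to 28 days before dosing. A subject who stops within about 4 weeks (8 weeks less 28 days) may therefore not need one, and a subject who dies or withdraws may have no such visit.

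A result near the boundary could then be read as pass or fail according to a set chosen after the data are seen.

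**Working it through.** **Inputs.** From protocol 8.3 and SAP 1.2.4: p0 = 0.10, p1 = 0.30, n1 = 18, r1 = 2, n = 35, r = 6. The unassessed share d is not in the documents; it is assumed at 2%, 5%, 10% or 20%.

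**1. The plan's own figures.** With X1 ~ Bin(18, p) and X2 ~ Bin(17, p):
- PET = P(X1 ≤ 2) at p = 0.10: 0.1501 + 0.3002 + 0.2835 = 0.734.
- Average N = 18 + (1 − 0.7338) × 17 = 22.53.
- P(X1 ≥ 3 and X1 + X2 ≥ 7) = 0.0474 at p = 0.10 and 0.9016 at p = 0.30, so beta = 0.098.

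All agree with the stated 0.734, 22.53, 0.047 and 0.098.

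**2. Rule on evaluable subjects, with 10% as the rate among treated subjects.** If unassessed subjects are non-responders, the rate among evaluable subjects is 0.10/(1 − d).
- Stage 1 pass is P(X ≥ 3) for X ~ Bin(18, 0.10/(1 − d)).
- Capped alpha: Stage 1 uses the first 18 evaluable subjects, the number treated to reach them is negative binomial, and the final count runs over 35 treated.
- Uncapped alpha: enrollment continues to 35 evaluable, about 35/(1 − d) treated.

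| d | Evaluable rate | Stage 1 pass | Alpha, capped at 35 | Alpha, 35 evaluable | Treated needed |
|---|---|---|---|---|---|
| 0 | 0.100 | 0.266 | 0.047 | 0.047 | 35 |
| 2% | 0.102 | 0.277 | 0.048 | 0.052 | 35.7 |
| 5% | 0.105 | 0.293 | 0.049 | 0.060 | 36.8 |
| 10% | 0.111 | 0.323 | 0.051 | 0.075 | 38.9 |
| 20% | 0.125 | 0.395 | 0.053 | 0.121 | 43.8 |

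Under the cap the final responder count is the same on either set, because unassessed subjects add no responders. Capped alpha therefore cannot exceed that of a single-stage test: P(X ≥ 7) for Bin(35, 0.10) = 0.055. The 2% row also illustrates the SAP's definition, if 2% remain unassessed for reasons other than progression or safety.

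**3. Rule on evaluable subjects, with 10% as the rate among evaluable subjects.** If 35 evaluable are reached, alpha stays at 0.047.

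**4. How likely the cap conflict is.** P(at least 1 of 35 unassessed) = 1 − (1 − d)^35 = 0.51 at 2% and 0.83 at 5%.

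**5. Cost of counting all treated subjects.** If 10% and 30% are treated-subject rates, alpha 0.047 and power 0.902 stand. If they are evaluable-subject rates, the treated rate is p(1 − d):

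| d | Alpha, all treated | Power, all treated | Power, Stage 1 on 18 evaluable, 35 treated in all |
|---|---|---|---|
| 5% | 0.038 | 0.869 | 0.881 |
| 10% | 0.029 | 0.828 | 0.851 |
| 20% | 0.016 | 0.718 | 0.760 |

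Most of the loss from 0.902 comes from the cap itself: at 10%, 0.902 − 0.851 = 0.051 of the total 0.902 − 0.828 = 0.074.

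**The case against.** - **Section 8.4.7 is the operative rule.** It is the specific analysis text, and enrolled in the sample-size sections may only describe accrual. This is a fair reading of the protocol alone. It still collides with the cap, and with a SAP that demotes and redefines the Response-Evaluable Set.
- **The SAP points to the Full Analysis Set by default.** It makes that set primary for efficacy. That is a reasonable inference, but no sentence applies it to the Simon count.
- **The cap may be soft.** The protocol foresees more than 35 evaluable subjects. If so, the larger alphas in the uncapped column become relevant. If the cap is hard, the provision for more than 35 can never apply.
- **The effect is small.** This largely stands for overall alpha under the cap. The values 0.060 to 0.121 need 10% to be a treated-subject rate, unassessed subjects to be non-responders, and enrollment past 35. Response is a secondary endpoint (protocol 8.1.2), and the synopsis lets the sponsor weigh durability, safety and competition before Stage 2. The Stage 1 effect remains.
- **Any single named set would cure the inconsistency.** True. The all-treated choice reverses protocol 8.2 and could cost power, down to 0.72 at 20% unassessed on evaluable-subject rates.
- **Timing.** Part 4 was to start only after CTCL Stage 1 enrollment closed, and SAP 1.2.5 already describes a Part 4 expansion. For CTCL the change is probably one of reporting only.
- **SAP 1.2.6 concerns reporting.** It may mean only that no interim report is planned, but it does not say so.

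**Conclusion.** The concern holds and should be fixed. The design arithmetic is right; the set to which it applies is not settled. The two documents disagree on the set for the rule, on the primary set for response, and on the definition of the Response-Evaluable Set.

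The main effect is at Stage 1. An inactive drug passes with probability 0.293 to 0.395 against the designed 0.266, for unassessed shares of 5% to 20%. Overall alpha moves little if 35 is a true cap (0.049 to 0.053). It is materially inflated only if enrollment continues to 35 evaluable subjects. These sizes assume that 10% is the uninteresting rate among treated subjects and that unassessed subjects are non-responders; the shares are assumed. If 10% was meant for evaluable subjects and 35 of them are reached, there is no inflation, but the conflict with the cap remains.

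**What to change.** 1. In both documents, apply both stages to the first 18 and first 35 treated subjects in each cohort. Count subjects with no post-baseline assessment as non-responders. This fits the cap, the SAP's primary set and the SAP 3.7.1 treatment of missing responses.
2. Use one definition of the Response-Evaluable Set in both documents and show it as a sensitivity analysis.
3. State the rule and its set in SAP 3.7.1.
4. Amend SAP 1.2.6 to except the Simon Stage 1 analysis of each Part 3 cohort from its statement on interim efficacy analyses.
5. Leave any Stage 1 decision already made, and report its count on both sets.

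The cost is wording in the synopsis, protocol 8.2, 8.3, 8.4.6 and 8.4.7, and SAP 1.2.6, 2 and 3.7.1. No extra patients or data are needed. If 10% and 30% were meant as evaluable-subject rates, the price is the power loss in step 5 of the working, and the documents should state which rates are meant.

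Naming the set does not settle what counts as a CTCL response. Protocol 7.14.1 gives both an any-organ and a global response, and the SAP 3.7.1 responder table has no row for the CTCL criteria. That needs its own sentence.
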